5.4.1. Inclusion criteria

HCPs must meet the following criteria to be eligible for inclusion in the survey:

- HCPs are aware of the insulin product Humalog U-200 KwikPen; and
- HCPs are involved in the treatment and management of patients with diabetes.

Patients must meet all of the following criteria to be eligible for inclusion in the survey:

- Patients are 18 years or older;
- Patients have diabetes; and
- Patients have filled at least one (1) prescription of Humalog U-200 KwikPen within the past 90 days.

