- Distribution of participants by years with diabetes
- Distribution of participants by length of time treated with any injectable insulin therapy
- Distribution of participants by length of time treated with Humalog U-200 KwikPen
- Distribution of participants by length of time of prior insulin use prior to Humalog U-200 KwikPen

Patient responses to questions pertaining to the survey objectives:

- Awareness of the Important Safety Information for Humalog U-200 KwikPen
- Receipt of or access to Important Safety Information
- Understanding of the key safety messages
- Self-reported practices with respect to the key safety messages

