5.11.1. Controls to minimize bias

A number of controls will be in place to ensure the survey is conducted in a professional manner and to minimize bias, including the following:

- Lists of response options will be randomized to minimize the potential for positional bias.
- The Internet and telephone surveys will be programmed to ensure that questions are asked in the appropriate sequence and all questions will be presented in a standard order to reduce exposure bias. Respondents cannot skip ahead or go back to a question once the question has been answered. All questions presented must be answered in order to complete a survey. Not all questions may be presented due to skip logic within the survey.
- Respondents will be provided with a unique code during the recruitment process and will then be asked to provide the unique code in order to gain access to the Internet-based and telephone administration systems. The code will be inactivated after use to minimize exposure bias and fraud.

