 - More than 15 years
 - I don't know

5. Do you use injectable insulin to treat your diabetes?
- Yes
 - No **[GO TO Q10, TERMINATE AFTER Q14]**
 - I don't know **[GO TO Q10, TERMINATE AFTER Q14]**
 - I don't have diabetes **[GO TO Q10, TERMINATE AFTER Q14]**
6. For how long have you been using injectable insulin to manage your diabetes?
- Less than 1 year
 - 1 – 5 years
 - 6 – 10 years
 - 11 – 15 years
 - More than 15 years
 - I don't know **[GO TO Q10, TERMINATE AFTER Q14]**
7. Have you been prescribed Humalog® U-200 KwikPen® at least once?
- Yes
 - No **[GO TO Q10, TERMINATE AFTER Q14]**
 - I don't know **[GO TO Q10, TERMINATE AFTER Q14]**
 - I don't have diabetes/I don't use insulin **[GO TO Q10, TERMINATE AFTER Q14]**

8. For how long have you been using Humalog® U-200 KwikPen®?
- I have not used the Humalog® U-200 KwikPen® yet
 - Less than 3 months
 - 3 – 6 months
 - 7 – 12 months
 - More than 1 year
 - I don't know
 - I don't have diabetes/I don't use Humalog® U-200 KwikPen® **[GO TO Q10, TERMINATE AFTER Q14]**
9. What type of mealtime insulin did you use prior to using Humalog® U-200 KwikPen®?
- Humalog® U-100 KwikPen®
 - Other 100 Units/mL insulin
 - I don't know
 - I don't have diabetes/I don't use Humalog® U-200 KwikPen® **[TERMINATE AFTER Q14]**
10. What is your gender?
- Male
 - Female

11. What is the highest level of education you have completed?

- Less than high school
- Some high school
- High school graduate/GED (General Education Diploma)
- Some college/Associate's degree
- Bachelor's degree
- Master's degree
- Professional or Doctoral degree
- Prefer not to answer

12. In what state do you live?

[DROP-DOWN LIST INPUT WITH STATES TABLE, EXCLUDE PREFER NOT TO ANSWER]

13. Which of the following groups best describes your age?

- Under 18 **[TERMINATE AFTER Q14]**
- 18 – 29
- 30 – 39
- 40 – 49
- 50 – 59
- 60 – 69
- 70 or older
- Prefer not to answer **[TERMINATE AFTER Q14]**

14. Have you or any of your immediate family members ever worked for Eli Lilly and Company (Lilly), United BioSource Corporation (UBC), or the Food and Drug Administration (FDA)?
- Yes **[TERMINATE]**
 - No
 - I don't know **[TERMINATE]**

[END SCREENING QUESTIONS]

[BEGIN SURVEY CONTENT]

[BEGIN PREAMBLE 2 – DISPLAY ON SAME PAGE AS NEXT QUESTION]

The following questions are about Humalog® U-200 KwikPen®.

[END PREAMBLE 2]

15. Please answer True, False, or I don't know for each of the following statements about Humalog® U-200 KwikPen®.

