	[RANDOMIZE LIST]	True	False	I don't know
A	Humalog® U-200 KwikPen® should only be injected using the prefilled KwikPen device in which it is supplied.			
B	Your dose of insulin does not need to be converted when changing from one strength of Humalog to the other (for example, changing from Humalog U-100 KwikPen to Humalog® U-200 KwikPen®).			

16. Please answer Yes, No, or I don't know for each of the following statements about the Patient Information Letter/*IMPORTANT SAFETY INFORMATION FOR* Humalog® KwikPen®, 200 units/mL, U-200 *insulin lispro* injection.

[RANDOMIZE LIST]		Yes	No	I don't know
A	The first time I was prescribed Humalog® U-200 KwikPen®, my doctor or nurse provided me with a paper copy of the Patient Information Letter/ IMPORTANT SAFETY INFORMATION . (This letter was included with the patient sample pen pack.)			
B	My doctor or nurse offered to explain information about the safe use of Humalog® U-200 KwikPen® the first time I was prescribed this product.			
C	I think about the important safety information for Humalog® U-200 KwikPen® to remind myself of the risks when injecting my insulin.			
D	I should always have a backup pen with me.			
E	It is ok to transfer insulin from the pen using a syringe.			

17. Other than the information you have received from your doctor or nurse, from what sources have you received and/or accessed information on the safe use and understanding of the Humalog® U-200 KwikPen®. (Please select all that apply.)

[RANDOMIZE LIST – KEEP OTHER AT THE BOTTOM]

- Pharmacist
- Other Healthcare Professional
- Diabetes Support Group
- Internet
- Product Warning Label
- Other

[TELEPHONE: BEGIN SAFETY EVENT/PRODUCT COMPLAINT – KEEP ON ONE PAGE]

(INTERVIEWER: Please record if respondent spontaneously reported a safety event or product complaint during the course of this interview.)

- Yes
- No **[GO TO CLOSING 1]**

Enter Safety Event or Product Complaint Verbatim

[MULTILINE INPUT]

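### Patient survey: Question 6 screens out eligible patients, Questions 9 and 17 lack a truthful response for some, the planned length-of-prior-use table has no source, and not-yet-users enter Question 16C

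*Protocol*

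**What the plan says.** **Eligibility.** Section 5.4.1 introduces its patient list with "Patients must meet all of the following criteria to be eligible for inclusion in the survey". The list has three items: adult age, diabetes, and the fill criterion "Patients have filled at least one (1) prescription of Humalog U-200 KwikPen within the past 90 days". Section 5.6 treats length of time on insulin as a demographic item, not a screening item.

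**Question 6 (Appendix I.3).** It asks "For how long have you been using injectable insulin to manage your diabetes", and its don't-know response carries the routing "I don't know [GO TO Q10, TERMINATE AFTER Q14". The don't-know responses on length of diabetes (Question 4) and length of U-200 use (Question 8) carry no termination. Question 8 also lets a patient who has not yet used the pen continue.

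**Question 9.** It asks "What type of mealtime insulin did you use prior to using Humalog® U-200 KwikPen". The responses are the U-100 KwikPen, another 100 units/mL insulin, don't know, and a response for people without diabetes or not using U-200, which terminates. Section 5.9 plans "Distribution of participants by length of time of prior insulin use prior to Humalog U-200 KwikPen", and Section 5.6 lists the matching variable specifically for mealtime insulin.

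**Question 16C.** It asks whether the patient thinks about the safety information when injecting, with responses Yes, No and don't know. The answer key in Appendix I.3 marks Yes as correct.

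**Question 17.** Apart from the doctor or nurse, it asks "from what sources have you received and/or accessed information on the safe use and understanding of the Humalog® U-200 KwikPen". Five named sources and an Other response are offered, with no none and no don't-know response.

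**Forced response.** Section 5.11.1 states: "All questions presented must be answered in order to complete a survey". Section 5.8 allows missing data only through skip patterns, and Section 6.2 restricts the analysis to completed surveys.

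**The concern.** Question 5 has already confirmed that the patient uses injectable insulin, so Question 6 has nothing left to screen. Its don't-know route still ends the survey for people who meet every stated criterion. They are told that they are not eligible, would enter the Section 5.9 count of ineligible patients, and cannot re-enter because the access code is inactivated after use. Recruitment aims at 280 completed surveys, so the loss would show in who is in the sample rather than in its size. If patients unsure of their treatment history also know the safety messages less well, the primary estimate of understanding is too favorable.

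The other items affect different results. Questions 9 and 17 leave some patients with no true response to give. One planned table has no source question. Question 16C takes answers about injecting from people who have not yet used the pen. None of this can be repaired in the analysis, because the responses were never offered or the patients were sent away.

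**Working it through.** **1. The plan's own precision.** Section 5.7, Equation 1: half-width = 1.96 × √(p(1 − p)/280). For p = 50, 60, 70, 80 and 90% this gives 5.86, 5.74, 5.37, 4.69 and 3.51 points. Table 1 prints 5.9, 5.7, 5.4, 4.7 and 3.5, so all five reproduce. They serve here only as a yardstick.

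**2. Question 6.** Let f be the share of eligible patients answering don't know, p₁ the correct rate among those who continue, and p₀ the rate among those terminated.

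- Rate in all eligible patients: (1 − f)p₁ + f·p₀
- Rate the survey observes: p₁
- Bias: p₁ − [(1 − f)p₁ + f·p₀] = f × (p₁ − p₀)

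The protocol gives neither f nor the gap. Assumed ranges are f = 1–10% and a gap of 0–30 points. Bias in points:

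| f | gap 0 | gap 10 | gap 20 | gap 30 |
|---|---|---|---|---|
| 1% | 0 | 0.1 | 0.2 | 0.3 |
| 2% | 0 | 0.2 | 0.4 | 0.6 |
| 5% | 0 | 0.5 | 1.0 | 1.5 |
| 10% | 0 | 1.0 | 2.0 | 3.0 |

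The largest value, 3.0, is below the smallest Table 1 half-width, 3.5. The bias is zero if the terminated patients are no different, and would be downward if they knew more.

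**3. Question 17.** Read the forced-response rule as requiring at least one tick. If a share s truly has no other source, each such patient either ticks something untrue or abandons the survey and leaves the analysis. The share of completers with at least one source is then 100% whatever s is. With a none response it would be 100% − s, which is 95% to 70% for an assumed s of 5% to 30%. Frequencies for single sources are not fixed in this way.

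**4. Question 9 against the planned table.** The question yields a type. Question 6 gives time on any injectable insulin in multi-year bands, and Question 8 gives time on U-200. Neither isolates the earlier mealtime insulin, so its length of use cannot be derived. For a patient with no earlier mealtime insulin, or one not at 100 units/mL, both substantive responses are untrue. Don't know is also untrue for someone who does know, and the last response terminates.

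**5. Question 16C.** Let u be the share of not-yet-users and q the Yes rate among users. If not-yet-users answer No, the overall Yes rate is q(1 − u), lower than q by q × u. For assumed q = 70–90%, the drop is:

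- u = 2%: 1.4–1.8 points
- u = 5%: 3.5–4.5 points
- u = 10%: 7–9 points

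**The case against.** The Question 6 effect is assumed in both size and direction. The protocol does not say how many patients would answer don't know, or that they know less. Even the top of the range is inside the planned precision. Section 5.3 judges success by whether a majority of respondents are aware, so a few points matter only near 50%. Section 5.9 requires reasons for ineligibility, and terminated patients still answer Questions 10 to 14, so their number and demographics would be visible. All of this stands as a limit on size. It does not make the termination consistent with Section 5.4.1, and the knowledge of the patients lost would remain unseen.

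A reader might infer that all four items bias understanding upward. They do not. The patient key messages are tested by Questions 15A, 15B, 16D and 16E. Questions 9, 16C and 17 do not enter those scores, so only Question 6 could move them.

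A reader might also infer that Question 16C forces an untrue answer. It does not, because No is available and can be true for someone who has not yet used the pen. The keyed answer is Yes, so the effect is downward.

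On Question 17, the protocol does not explicitly plan an any-source summary. Receipt of the patient letter is measured by Question 16A. The product warning label is a listed source, and Section 3.1 says that the pen carries warnings, so the share with no source may be small. What stands is that a patient without one has no true response.

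On Question 9, U-100 users who switched have exact responses, and a don't-know answer lets others continue, so nobody need be lost. The item remains wrong for patients whom it does not fit. It could also be argued that Section 5.9 omits the word mealtime, so that Questions 6 and 8 together might serve. But Section 5.6 specifies mealtime insulin, and Section 5.9 already has a separate line for any injectable insulin.

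**Conclusion.** The point holds as a set of questionnaire faults that should be corrected before launch. Question 6 contradicts the stated eligibility criteria and miscounts eligible patients as ineligible; this needs no assumption. Any upward bias in understanding comes from that item alone and is of unknown size: 0 to about 3 points under the assumed 1–10% affected and 0–30 point gap. The documents do not establish that it occurs. Question 17 makes an any-source figure 100% among completers, provided that the forced-response rule requires at least one tick. Question 9 lacks a truthful response for some patients and cannot supply the planned length-of-use distribution. Not-yet-users can lower the Question 16C result by q × u, with u and q both unknown. The statistical analysis plan is not at hand, but no analysis can recover patients who were terminated or responses that were not offered.

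**What to change.** - **Question 6:** remove the termination from the don't-know response, so that it continues as at Questions 4 and 8.
- **Question 17:** add a none-of-these response and a don't-know response, each exclusive of the other choices.
- **Question 9:** add a response for no earlier mealtime insulin and an Other response. Then either replace the length-of-prior-use item in Sections 5.6 and 5.9 with type of prior insulin, or add a question on duration.
- **Question 16C:** skip it for patients who say at Question 8 that they have not yet used the pen, and leave them out of the 16C denominator only. Dropping them from other results would remove patients who are eligible under Section 5.4.1.

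The cost is a few response options and routing edits, a matching change to the table list, and an IRB notification before launch. Sample size and analysis method do not change.

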5. RESEARCH METHODS

5.1. Study Design

This study will be observational and cross-sectional in design. Separate surveys will be administered to HCPs involved in the treatment and management of patients with diabetes and to patients with diabetes who have been prescribed Humalog U-200 KwikPen. The study has been designed and will be executed and analyzed in collaboration with United BioSource Corporation (UBC). The surveys have been developed to enable the study objectives to be met.

Qualitative Research (also known as User Testing) was performed on each survey with a sample of 12 HCPs and 9 patients. The Qualitative Research procedure was designed to assess comprehension among patients regarding the words and phrases used in select survey questions and response options. Qualitative Research also assessed the clarity of the survey questions as presented to HCPs and the interest and acceptance of the surveys among all prospective respondents, flow and ease of completing the surveys, and preferred modes of administration. Findings and recommendations from Qualitative Research have been incorporated into the surveys

Assessment of the additional risk minimization measures in the participating samples will be used to determine whether the target populations are aware of and adherent to the key safety message themes regarding the risk of hypoglycemia and/or hyperglycemia attributed to medication errors or misuse associated with the administration of Humalog U-200 KwikPen. All statistical analyses will be descriptive, i.e., no formal hypothesis will be tested.

HCPs:

HCPs will be identified through Lilly's list of HCPs who were targeted for the DHPC. Surveys targeting eligible HCPs will be administered via two modalities: 1) Internet, which will allow respondents to participate at a time and location that is convenient for them, or 2) by telephone to allow participation by respondents who may not have Internet access. Each invitation will

include information on how to access the online survey and provide the toll-free number for accessing the telephone survey. Both modalities will offer the same survey.

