5.4.2. Exclusion criteria

HCPs meeting any of the following criteria will not be included in the survey:

- HCPs who are not involved in the management of patients with diabetes
- HCPs who have ever worked for or who have had family members who have ever worked for Lilly, UBC, or the FDA will be excluded.

Patients meeting any of the following criteria will not be included in the survey:

- Patients with diabetes who have not been prescribed Humalog U-200 KwikPen
- Patients who have ever worked for or who have had family members who have ever worked for Lilly, UBC, or the FDA will be excluded.

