5.6. Data sources

In this survey, the data source for HCPs will be Lilly's list of HCPs who received the DHPC. From this data source HCPs will be invited to participate in the survey. The data source for patients will be the PBM's prescription data identifying those patients who have filled/refilled a prescription of Humalog U-200 KwikPen within 90 days prior to survey launch.

Structured questionnaires ([APPENDIX I.1](#) and [APPENDIX I.3](#)) comprised of closed-ended questions or statements with multiple response choices (i.e., questions or statements asking the respondents to choose from a defined list of responses) will be used to collect the survey data. The surveys will collect data on respondent characteristics and their responses to the risk understanding questions. The data collected from the surveys will be used to inform the evaluation of the effectiveness of the risk minimization measures.

Each survey will begin with a screening module with questions to confirm eligibility. Depending on the answers to the screening questions, survey participation will either be terminated or continued. If ineligible, the respondent is immediately notified with a "thank you" message that survey participation has ended. If eligible, the respondent is allowed to continue survey participation.

HCPs:

Screening questions:

- Agreement to participate
- Involved in the management of patients with diabetes
- Employment by Lilly, UBC, or the FDA
- Awareness of Humalog U-200 KwikPen

Data on demographic characteristics:

- Age
- Gender
- Role at facility
- Facility type
- State of practice

- HCP medical specialty (e.g., endocrinology, primary care)
- Number of years practicing medicine/nursing
- Number of Humalog U-200 KwikPen-treated patients the HCPs prescribed to or managed in the 12 month period preceding the survey (self-reported)

Data pertaining to evaluation of the effectiveness of the risk minimization measures:

The survey includes questions/statements that will assess the understanding or the risks and associated behavior of the HCPs to minimize these risks. The understanding level and behaviors will be analyzed using descriptive statistics and confidence intervals (CIs) and will be used to determine the effectiveness of the risk minimization measures:

- Awareness of the DHPC on the correct use of Humalog U-200 KwikPen
- Understanding of the key safety messages

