- Self-reported practices with respect to communication of the key safety messages in clinical practice

Patients:

Screening questions:

- Agreement to participate
- Diagnosis of diabetes
- Filled a prescription for Humalog U-200 KwikPen within the past 90 days prior to survey launch
- 18 years or older
- Employment by Lilly, UBC, or the FDA

Data on demographic characteristics:

- Age
- Gender
- State
- Employment status
- Length of time with diabetes
- Length of time on any insulin therapy
- Length of time on Humalog U-200 KwikPen
- Length of time on mealtime Insulin used prior to Humalog U-200 KwikPen

Data pertaining to evaluation of the effectiveness of the risk minimization measures:

The survey includes questions/statements that will assess the risk understanding and behavior of patients. The understanding level and behaviors will be analyzed using descriptive statistics and CIs and will be used to determine the effectiveness of the risk minimization measures:

- Awareness of the Important Safety Information for Humalog U-200 KwikPen
- Receipt of or access to the Important Safety Information
- Understanding of the key safety messages
- Behavior with respect to the key safety messages

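### The patient screener (Q5, Q8, Q9) adds a current-use condition that the eligibility criteria do not contain, so eligible patients who stopped or switched back are likely to be ended early or mixed with current users

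*Protocol*

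**What the plan says.** **Eligibility in the protocol body.**

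- Section 5.1 surveys "patients with diabetes who have been prescribed Humalog U-200 KwikPen".
- Section 5.4.1 asks for adults with diabetes and adds "Patients have filled at least one (1) prescription of Humalog U-200 KwikPen within the past 90 days".
- Section 5.4.2 has two patient exclusions. One is "Patients with diabetes who have not been prescribed Humalog U-200 KwikPen"; the other concerns employment by the sponsor, the survey vendor or the FDA.
- Section 5.6 draws patients from pharmacy-benefit data on "those patients who have filled/refilled a prescription of Humalog U-200 KwikPen within 90 days prior to survey launch", and its screening list has the item "Filled a prescription for Humalog U-200 KwikPen within the past 90 days prior to survey launch".

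None of these requires the patient still to be using the pen.

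**Screener in Appendix I.3.**

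- Q5 asks "Do you use injectable insulin to treat your diabetes". Every answer except Yes leads to termination after Q14.
- Q7 asks "Have you been prescribed Humalog® U-200 KwikPen® at least once". A former user can truthfully answer Yes and continue.
- Q8 asks "For how long have you been using Humalog® U-200 KwikPen". The options are not yet used, four durations, don't know, and a merged option for having no diabetes or not using the pen. Only the merged option terminates.
- Q9 asks which mealtime insulin came before and offers the same merged option, again terminating.

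The survey legend says that an answer with no skip instruction continues to the next question. Section 6.2 analyses completed surveys only.

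**The concern.** A patient can meet every criterion in 5.4.1 and still be told by the screener that they are not eligible. The rule that removes them is written nowhere in the criteria, and it treats a patient who filled but has not yet used the pen more leniently than one who used it and stopped.

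Former users matter to the study question. Section 3.1 gives the reasons for the risk minimization measures: insulin drawn out of the cartridge when the device malfunctions, and dose adjustment when moving between strengths. Someone who moved from U-100 to U-200 and back has changed strength twice, so the dose-conversion statement (Q15B) bears directly on them.

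Section 4 speaks of a representative population from which to generalize, and section 5.11 describes the patients simply as those who filled or refilled. Neither mentions a restriction to current users. Terminated respondents never see Q15 and Q16, so no later analysis can recover their answers.

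**Working it through.** **1. Trace of the skip logic.** Each patient below is an adult with diagnosed diabetes, a qualifying U-200 fill and no disqualifying employment, and so is eligible under 5.4.1 and 5.4.2.

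| Patient | Answers | Outcome |
|---|---|---|
| Stopped all injectable insulin | Q5 No | Terminated after Q14 |
| Back on U-100, answers Q8 as a non-user | Q5 Yes, Q7 Yes, Q8 merged option | Terminated after Q14 |
| Back on U-100, picks a duration, then the merged option | Q5 Yes, Q7 Yes, Q8 duration, Q9 merged option | Terminated after Q14 |
| Back on U-100, picks a duration, names a prior insulin | Q5 Yes, Q7 Yes, Q8 duration, Q9 insulin type | Kept; cannot be told from a current user |
| Filled, not yet used, names a prior insulin | Q5 Yes, Q7 Yes, Q8 not yet, Q9 insulin type | Kept |
| Does not know the duration, names a prior insulin | Q5 Yes, Q7 Yes, Q8 don't know, Q9 insulin type | Kept |

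The Q8 stem screens nobody out; its last answer option does. Loss of a former user at Q8 is therefore likely, not certain. Respondents cannot return to an answered question (5.6.1, 5.11.1).

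**2. Time in which stopping can occur.** The fill window is 90 days before launch (5.6). Data collection is estimated for August to November 2016 (section 3). Assuming 1 August to 30 November, collection lasts 121 days, so the longest gap from fill to response is 90 + 121 = 211 days. The protocol gives months only, so this is an approximate maximum.

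**3. The plan's precision.** Equation 1 in 5.7 at 80% correct and n = 280 gives 1.96 × √(0.80 × 0.20 / 280) = 0.0469, or 4.7 points, as in Table 1. The other four rows also reproduce (5.9, 5.7, 5.4 and 3.5 points). The screening conflict does not affect Table 1 or the target of 280.

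**4. Possible shift in an understanding rate.** Let s be the share of eligible patients screened out, and d the correct-answer rate in those kept minus that in those lost. Then shift = s × d. The documents give neither quantity. Assume s = 5-20% and d = 10-30 points, with every former user lost:

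- Smallest: 0.05 × 10 = 0.5 points.
- Middle: 0.10 × 20 = 2.0 points.
- Largest: 0.20 × 30 = 6.0 points.

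For the shift to equal the 4.69-point half-width, s must be 4.69/30 = 16%, 4.69/20 = 23% or 4.69/10 = 47% for d = 30, 20 or 10 points. Within the assumed range, only the upper corner exceeds the sampling error. If d were negative, the shift would run the other way.

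**The case against.** The strongest defence is that part of the study concerns behaviour during administration (sections 4 and 5.3), so limiting it to current users is a reasonable choice. That stands as a design option. But the criteria do not state it, and the not-yet-used answer at Q8 does not fit it.

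Three stronger readings are tempting, and the documents do not support them.

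- A reader might infer that the results describe persistent users only. They do not. Not-yet-users, users of less than three months and those answering don't know can all pass Q8, no minimum duration applies, and a former user may choose a duration and stay in.
- A reader might infer that understanding will look better than it is. The documents give no stopping rate, no reasons for stopping and no understanding by use status, so even the sign is unknown.
- A reader might infer that the report of ineligibility reasons in 5.9 would hide the loss because the Q8 option merges two reasons. Largely it would not. Reaching Q8 requires Yes at Q3, Q5 and Q7, so those who terminate at Q8 are nearly all prescribed insulin users who say they do not use the pen. Q5 lists No separately from having no diabetes. Terminations tabulated by question would show most of the loss. They would not show former users who chose a duration, and they would not supply the missing Q15 and Q16 answers.

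**Conclusion.** The conflict holds. The criteria rest on a prescription or a 90-day fill, while the screener adds current use at Q5, Q8 and Q9. Q8 gives a patient who stopped or switched back no accurate answer that continues. The patient results may therefore under-represent former users without saying so, and those who remain cannot be identified.

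The routing itself can be read directly from the protocol. The effect on understanding cannot: 0.5 to 6.0 points is an illustration that rests on 5-20% stopping, understanding 10-30 points lower in those who stopped, and loss of all of them. It is worth correcting before the survey is programmed, because analysis cannot repair it afterwards.

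**What to change.** Choose one of two routes and make the criteria and screener agree.

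**Keep former users, as the criteria now imply.**

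- Q8: add a non-terminating answer for having used the pen but no longer using it.
- Q9: make the merged option non-terminating for respondents who gave that answer.
- Q5: route No to Q7.
- Q7: remove or split off the not-using-insulin part of its terminating option; otherwise a patient rerouted from Q5 can be ended there.
- Skip Q16C for former users, since it asks in the present tense about injecting.
- Keep former users in the understanding and receipt results (Q15A, Q15B, Q16A, Q16B, Q16D, Q16E), and report current and former users separately.

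**Restrict to current users, if that is the intention.** State current use in 5.4.1 and narrow the population claimed in sections 4 and 5.11.

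The first route costs edits to answer options and skips at Q5, Q7, Q8 and Q9, one skip at Q16C and one extra table split. Its downside is a slightly more mixed sample. The second costs text changes only, but gives up conclusions about patients who stopped.
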